- Willing to be randomized per this protocol; each patient will be questioned as to their willingness to stay in the trial regardless of the group to which group they are randomized.
- Willing to follow the protocol
- Able to undergo a brain MRI without anesthesia

* Continuously will be defined as no less than 75% of all prescribed doses, with no time of greater than four weeks from last intended dose to have missed a dose (8 weeks for natalizumab, i.e. one missed dose).

Exclusion criteria:

- Any MS relapse in the last five years, as determined at the screen visit by the PI
- Any new or definitely enlarging T2/FLAIR lesion or new gadolinium-enhancing lesion within the past three years (at least two scans separated by at least three years must be reviewed, with the most recent scan being no more than 6 months prior to randomization) on brain or spine MRI scan. Lesions must be 3mm or larger to be exclusionary.
- Significant (as defined by the PI) intolerance of presently-used DMT
- Use of any non-FDA-approved DMT in the last 5 years.

- More than two courses of acute, systemic (IV or oral) steroids in the last 5 years or any use within the last year. Course is defined as three or more days continuously, and not to exceed 14 days. No use of chronic, systemic steroids, defined as 15 or more days, in the last 5 years. Any use of steroids to treat MS relapse, possible relapse, or pseudo-relapse in the last 5 years. Inhaled or topical steroids are not exclusionary.
- Prior use of alemtuzumab, mitoxantrone, cyclophosphamide, methotrexate, cyclosporine, rituximab, siponimod, or cladribine in the last 5 years
- Prior use of any experimental agent used as a DMT for MS in the last five years
- Other significant medical or psychiatric illness, if uncontrolled. Examples: uncontrolled hypertension, uncontrolled diabetes, uncontrolled asthma, uncontrolled depression
- Cancers other than basal cell skin cancers within the last 5 years
- Unable to give informed consent or follow the protocol
- Unable to undergo brain MRI
- Unwilling to be randomized per this protocol
- History of other chronic neurological illnesses that might mimic MS with chronic or intermittent symptoms (i.e. ALS, myasthenia gravis, chronic neuropathy, etc.)

C. Study Design and Research Methods

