their primary neurologist for consideration of restarting a MS DMT of their choice, or switching to an alternative DMT (if they were in the continuation arm). They will continue to be followed at all study time points with all procedures. This is a pragmatic trial, so individuals will continue to receive care from their primary neurologist (in many cases, this will be the Treating physician/PI as well). At all times, it will remain the choice of the patient and their physician to maintain or change the MS DMT. Any worsened neurological symptoms attributed to MS that are treated with systemic steroids, regardless of characterization above, will be counted as a Protocol defined relapse. In this context, it is imperative that patients contact the local PI of the study first and foremost, so that decisions about the use of steroids may be made by study personnel, and steroids used or not used after the determination of relapse status per the protocol.

An adverse event (AE) is the appearance or worsening of any undesirable sign, symptom, or condition occurring after starting the study even if the event is not considered to be related to study conditions or assignment. Study conditions or assignment includes assignment to continue or discontinue prior DMT. Medical conditions and diseases present before starting the study are only considered AEs if they worsen after starting the study. Abnormal laboratory values or test results constitute AEs only if they induce clinical signs or symptoms, are considered clinically significant, or require therapy.

The occurrence of AEs should be sought by nondirective questioning of the patient at each visit during the study. Adverse events also may be detected when they are volunteered by the patient during or between visits or through physical examination, laboratory test, or other assessments. All AEs must be recorded in the AEs eCRF with the following information:

1. the severity grade (mild, moderate, or severe)
2. its relationship to the study drug(s) (suspected/not suspected)
3. its duration (start and end dates or if continuing at final examination)
4. whether it constitutes a serious AE (SAE)

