Serious adverse events such as hospital admissions for > 24 hours, new significant medical diagnoses such as cancer (other than basal cell carcinoma), and MS relapse requiring corticosteroid use will be ascertained at each visit. SAEs should be reported to sponsor and entered into the electronic database within 24 hours of the event being reported to the study team. We will collect ongoing side effects of all DMTs, and non-serious adverse events in both groups, and report descriptive statistics and proportions on all adverse events. We will provide confidence intervals for the proportions and test them between treatments groups using the same type of methods used for the primary outcome.

E. Potential Scientific Problems:

Blinding of outcome measures is very important. As this is a pragmatic study, in which the research component is added on to the basic clinical visit, the Treating Physician/PI will have obtained a relapse history as part of that routine visit, yet is not blinded to the patient's medication assignment. The definition of relapse includes performance of the EDSS, and the separate EDSS Examining Clinician will be blinded to medication assignment, as well as to the relapse history, when doing the EDSS. While it might be preferential to have a relapse assessor separate from both the PI and the EDSS rater, this is impractical due to costs, the requirement to have a third clinician available at the visit, and the extra time of the visit. Thus, we will ask the PI to do a relapse assessment based on symptoms, but only make this information available to the EDSS Examining Clinician AFTER the EDSS is completed. The EDSS Examining Clinician will make the final assessment as to whether a Protocol defined relapse has occurred. While MRI readers and Examining Clinicians will be blinded to the patient's medication assignment, patients will not be blinded to medication assignment. Thus interpretation of the secondary Aims and Hypotheses as they relate to PROs will be potentially confounded by patient bias.

Significant efforts will be made to enroll only those patients who are truly willing to be randomized. If an excessive number of patients enter the study attempting to get into one or the other group assignment, they may be more likely to drop out if they do not receive the desired assignment, thus confounding data analysis.

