It is possible a patient may have asymptomatic changes on a surveillance spine MRI scan, which is not part of the protocol or SOC. Most new spine lesions will have clinical symptoms and signs associated with them, however, limiting the significance of this issue.

F. Data Analysis Plan:

- a. Aim #1: Proposed Data Analysis: We will perform a non-inferiority test for the proportions of the discontinue and continue groups experiencing a binary, protocol-defined disease event within a year. A countable event will be a new protocol-defined relapse, and/or a new brain MRI lesion. We will test the null hypothesis of inferiority with the proportion of disease events for the discontinue group being 0.08 greater (i.e., 0.10 vs 0.02) than the proportion for the continue group under the alternative that the two rates are equal. Because of the expected small numbers of events, we expect to use likelihood based exact binomial methods to obtain a confidence interval for

comparing the proportions. If the upper bound of the 95% confidence interval for the difference between the groups is less than 0.08, then we can rule out discontinuation increasing the disease event proportion by 0.08 or greater. The anticipated small number of events, and the need to use exact methods, will constrain the models that can be used in analyses. Adjustment for center heterogeneity may be attempted with Cochran-Mantel-Haenszel test, but may be similarly limited by anticipated small number of events. We will also calculate estimates and confidence intervals, using exact methods as necessary, for the proportion of disease events in both the discontinue and continue groups. In the unlikely event the proportions are relatively large, we will also calculate estimates and confidence intervals for relative risks. Larger numbers of events would permit the fitting of more complex models

b. Aim #2: Proposed Data Analysis: We will calculate estimates and confidence intervals, using exact methods as necessary, for the proportion of disease events in both the discontinue and continue groups. Aim #2 assesses progression of disability as noted on the EDSS, and this will be defined as an increase of at least one point, confirmed at 6 months, for those with a baseline EDSS ≤ 5.5 , or a change of at least 0.5 for those with EDSS of 6.0 or greater at baseline. Outcomes assessed will include % of patients with confirmed progression in each group and mean change in EDSS in each group.

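### DMT may be changed at any time, but the Aim 1 non-inferiority comparison names no analysis set and includes no check on treatment received, so crossover before an event could favour declaring discontinuation safe

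*Combined protocol and SAP*

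**What the plan says.** Section III.D (Risks/Safety) leaves treatment open in both arms, whether or not an endpoint has occurred: "At all times, it will remain the choice of the patient and their physician to maintain or change the MS DMT". A patient who reaches an endpoint is referred back to the primary neurologist to consider restarting or switching, and follow-up goes on: "They will continue to be followed at all study time points with all procedures".

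Section III.F, Aim #1, sets out the primary analysis: "We will perform a non-inferiority test for the proportions of the discontinue and continue groups experiencing a binary, protocol-defined disease event within a year". The claim is made on this condition: "If the upper bound of the 95% confidence interval for the difference between the groups is less than 0.08".

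No section names an analysis set, whether intention-to-treat, per-protocol or on-treatment. None says how to handle a patient who restarts or stops a DMT before any event. The planned variations are wider relapse definitions (III.D), a possible centre adjustment (III.F) and subgroups (Sample Size Estimation). None of these concerns treatment received.

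Section III.B defines continuous DMT use for entry: "Continuously will be defined as no less than 75% of all prescribed doses", with limits on gaps. Nothing applies that definition after randomisation. Table 1 schedules Prior/Con Meds at every visit and at the monthly calls.

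**The concern.** The main hypothesis is that these patients may safely discontinue. A discontinue-arm patient who resumes a DMT in month 2 and is event-free at month 12 counts towards that conclusion. A continue-arm patient who stops early counts as evidence about staying on drug. In a superiority trial such mixing works against the claim. In a non-inferiority trial it works for the claim whenever the true effect is harmful.

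Some restarts may also be related to risk. A suspected or out-of-window relapse is not a primary event unless systemic steroids are given, yet it could prompt a restart. What is at stake is whether a result inside the margin describes stopping DMT, or being assigned to stop with freedom to resume.

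**Working it through.** **Inputs from the plan** (Sample Size Estimation and Aim #1): n = 112 per arm; margin 0.08; alpha 0.025, one-sided; null 0.10 versus 0.02; alternative 0.02 versus 0.02; stated power 95%.

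**Assumptions, not in the documents:** a fraction c of the discontinue arm restarts and a fraction d of the continue arm stops, before any event and unrelated to risk. A fraction f of the year is spent on the other treatment (f = 1 for crossover at the start). Each patient carries the risk of the treatment actually in use.

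**Tests.** Let x and y be the event counts, with observed proportions a = x/n (discontinue) and b = y/n (continue). Let a0 and b0 be the maximum-likelihood values constrained to a0 − b0 = 0.08.
- Score: z = (a − b − 0.08) / √[a0(1 − a0)/n + b0(1 − b0)/n].
- Likelihood ratio: z = −√(2[logL(a,b) − logL(a0,b0)]) when a − b < 0.08, positive otherwise.

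Non-inferiority is declared if z ≤ −1.96. Probabilities are binomial sums over all (x, y).

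**Plan's own figures first.** At 0.02 versus 0.02 with 112 per arm, power is 94.95% by likelihood ratio, which matches the stated 95% and the likelihood-based wording of Aim #1. The score test gives 90.7%. The score test does reproduce the subgroup figures at 56 per arm: 59.4% (stated 59%) at margin 0.08, and 84.0% (stated 84%) at margin 0.13 − 0.02 = 0.11. Both tests are therefore shown.

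**Effect of crossover at the null.**

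Discontinue risk = 0.10 − 0.08·c·f. Continue risk = 0.02 + 0.08·d·f.

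Example with c = d = 0.10, f = 1: 0.10 − 0.008 = 0.092 and 0.02 + 0.008 = 0.028, difference 0.064.

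| Scenario | Risks | Difference | False non-inferiority: score | Likelihood ratio |
|---|---|---|---|---|
| No crossover | 0.100 / 0.020 | 0.080 | 1.9% | 2.9% |
| 10% restart, early | 0.092 / 0.020 | 0.072 | 3.3% | 5.0% |
| 15% restart, early | 0.088 / 0.020 | 0.068 | 4.3% | 6.5% |
| 10% in each arm, early | 0.092 / 0.028 | 0.064 | 5.6% | 7.6% |
| 10% in each arm, f = 0.5 | 0.096 / 0.024 | 0.072 | 3.3% | 4.8% |
| 20% in each arm, early | 0.084 / 0.036 | 0.048 | 13.3% | 16.5% |
| 30% restart, early | 0.076 / 0.020 | 0.056 | 9.2% | 13.4% |

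The target is 2.5%. The likelihood-ratio test already sits at 2.9% without crossover, so its rows should be read against that.

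**When there is no dilution.** If the true risks are equal, the 0.08 in both formulas becomes 0 and crossover changes nothing. A DMT change after a counted event leaves the binary outcome as it was. A change from one DMT to another does not move a patient off drug.

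**On-assigned-treatment analysis.** With 10% of each arm removed (112 × 0.9 ≈ 101 per arm) and crossover unrelated to risk, false non-inferiority returns to 1.7% (score) or 3.0% (likelihood ratio). Power at 0.02 versus 0.02 is 87% or 92%, against 91% or 95% at 112.

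**The case against.** The strongest reply is that this is a pragmatic trial. Its natural question is the effect of assigning discontinuation with freedom to resume, and for that question a comparison by randomised group has its planned error rate. This stands. A reader might infer from the table that the 0.025 level is breached outright. It is exceeded only for the effect of actually stopping versus actually continuing, and only if stopping raises risk. But the plan never says which question it answers, or that groups are compared as randomised. That is the natural reading and it is not written down.

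The plan also limits departures. Section III.B questions each patient about staying in whichever group is assigned, and it excludes significant intolerance of the current DMT. Steroid-treated worsening counts as a relapse whatever its category. The secondary analyses with wider relapse definitions would count many of the episodes that might prompt a restart. These points reduce the concern, but none of them examines treatment received.

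A reader might also infer that the plan expects crossover, since Section III.E warns of patients seeking one arm: "they may be more likely to drop out if they do not receive the desired assignment, thus confounding data analysis". The text does not support that. The warning is conditional, and it concerns dropout.

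Finally, an on-treatment analysis has selection bias of its own. This is why it should support the randomised comparison and not replace it.

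**Conclusion.** The point holds as a gap in the analysis plan. Treatment is open at all times, the primary analysis set is unnamed, and nothing checks treatment received in a trial where pre-event crossover would favour the claim if stopping is harmful.

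The size is conditional. The crossover rates are assumed, and early crossover is the upper end for a given rate. With 10% in each arm, the error for the effect of actual exposure is 5.6% (score) or 7.6% (likelihood ratio) if crossover is early, and 3.3% or 4.8% at half exposure. Risk-related restarts could make it larger. The documents do not show that crossover will be common or that the trial's conclusion will be wrong.

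**What to change.** 1. State that the primary Aim 1 comparison is by randomised group.
2. Pre-specify one supportive on-assigned-treatment analysis of the same one-year endpoint against the same 0.08 margin. Identify departures from the Prior/Con Meds records. For the continue arm, apply the Section III.B definition of continuous use. For the discontinue arm, use any DMT resumption before an endpoint.
3. State how event-free departures enter the denominator. Two workable options are to restrict both arms to patients on assigned treatment until first event or month 12, or to censor at departure and compare one-year cumulative risk.
4. Attribute a lesion found at the first MRI after a departure to the assigned treatment. Lesions are seen only at scans, and discarding one that formed off drug would itself favour discontinuation.
5. Report departures by arm, date and reason, and qualify any claim that discontinuation is safe if the two analyses disagree.

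A sensitivity analysis counting every restart as an event is not worth adding. With equal true risks of 0.02, non-inferiority would be declared only about 14% of the time with 5% restarts (0.02 + 0.98 × 0.05 = 0.069 versus 0.02) and 0.5% with 10% (0.118 versus 0.02), by score.

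The cost is analysis-plan wording and one extra analysis on data already scheduled. That analysis has its own selection bias and the somewhat lower power shown above. No visit, sample size or clinical rule changes.

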This will be a randomized discontinuation trial (RDT).⁷¹ While RDTs have been done in cancer^{72,73} and rheumatoid arthritis patients,⁶⁶ this would be the first such study in MS. Patients will be randomized to either continue with their present MS DMT (control), or discontinue their present DMT (experimental), in a 1:1 fashion using the Interactive Voice Response System (IVRS) randomization system. A total of up to 265 patients will be consented and enter the trial. After allowing for up to 15% dropout rate, we aim for 225 (112 in each group) patients to complete the study. Patients enrolled after July 31, 2019 will not complete the full two years of assessments; study follow up will only continue until September 1, 2021. There will be no placebo, and no sham treatment. There will be no taper period. (Please see the statistics sections for power analyses).

At each site, extensive chart review will be used to identify eligible patients. Patients will be approached at their next standard of care clinical visit by their primary neurologist and/or a study coordinator about participating in the study. Either the patient's primary neurologist or the study PI will verify inclusion/exclusion criteria and ensure that all patient's questions are answered before consent is signed. Study information may be distributed in the community in order to recruit participants from other sources. Patients who do not receive their standard neurological care at the study site will be encouraged to transfer their neurological care to the study site for the duration of the study. If this is not possible, these subjects must agree to have standard of care MRIs done by their primary neurologist yearly throughout the study and have the results sent to the study site. MRIs at the 6-month time point must be conducted at the study site. All research visits will be conducted at the same time as SOC visits when possible, or as separate visits if not possible.

Please see Table 1 below for the schedule of study activities.

Table 1: Schedule of Research Assessments

MS Patients consented for the study	T ₀ (Baseline)	T ₁ (6 Months +/- 1 week)	T ₂ (12 Months +/- 1 week)	T ₃ (18 Months +/- 1 week)	T ₄ (24 Months +/- 1 week)***	Unscheduled Visit*	Phone follow-up (monthly +/- 1 week)
Informed Consent	X	-	-	-	-	-	
Inclusion/Exclusion	X	-	-	-	-	-	
Physical Exam/ MS Medical History	X	-	-	-	-	-	
Vitals	X	X	X	X	X	X	
Prior/Con Meds	X	X	X	X	X	X	X
Adverse Events	X	X	X	X	X	X	X

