Comorbidities	X	X	X	X	X	X	
Neuro-QoL Short Form	X	-	-	****	X	X	
PDSS	X	X	X	X	X	X	
SymptoMScreen	X	X	X	X	X	X	
MSIS-29	X	X	X	X	X	X	
SDMT	X	X	X	X	X	X	
Treatment Satisfaction Question	X	X	X	X	X	X	
Relapse Assessment	X	X	X	X	X	X	
EDSS (by unbiased Rater)	X	X	X	X	X	X	
Treatment Decision Questions	-	-	-	****	X	X	
MRI**	X	X	X	****	X	-	

*Unscheduled visits may occur for patients during the study. If an MRI is requested by the PI in relation to an unscheduled visit, that MRI would be paid through standard of care.

**T₀, T₂, and T₄ MRIs paid as part of standard of care (SOC). T₁ MRI paid as research only and must be performed at the study site. T₀ Brain MRI to be performed within 6 months preceding study entry, and will be reviewed and confirmed as fulfilling entry criteria. If T₀ MRI results for a potential subject from within the last 6 months are not available, the patient should be scheduled for a Standard of Care MRI and these results should be reviewed for inclusion/exclusion criteria prior to enrollment into the study and completion of Baseline visit.

***Participants enrolled after July 31, 2019 may not complete T₄, but will be followed until September 1, 2021. If T₃ is on or before June 30, 2021, participant should come in for an out of window T₄ visit before Sept. 1, 2021.

****If T₃ falls after June 30, 2021, participants will not come in for a T₄ visit, but will complete a NeuroQoL and Treatment Decision Question during T₃, and will have an out of window Month 24 MRI.

After thorough discussion of the trial and signing an informed consent, participants will be seen at five specified time points: T₀, screen/baseline; T₁ at 6 months; T₂ at 12 months; T₃ at 18 months; and T₄ at 24 months. Patients will be screened, have a baseline brain MRI reviewed, undergo a relapse assessment and EDSS exam, complete all PROs, and be randomized at T₀. They will be examined every 6 months at times T₀, T₁, T₂, T₃, and T₄ and undergo MRI scans of the brain at times T₀, T₁, T₂, and T₄. If T₃ occurs after June 30, 2021, participants will not be seen for a T₄ visit and they will complete the NeuroQoL and Treatment Decision Question during T₃. If the T₃ visit occurs on or before June 30, 2021, the patient will be brought back in for a T₄ visit prior to September 1, 2021. Patients who have finished the study prior to protocol v. 10Jan2020 approval will be contacted via phone to obtain verbal consent, and will then be asked the Treatment Decision Question.

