c. Aim #3: Proposed Data Analysis: Descriptive statistics on patient demographics, PDSS, MSIS, performance and NeuroQOL short form scales, and all other PROs will be prepared for treatment group by occurrence of disease event, and qualitatively compared. Pre-Post change will be compared between treatment groups. Change scores will be used for continuous and metric outcomes, and the treatment groups will be compared with two sample T-tests, or Wilcoxon tests if necessary. Binary outcomes, such as dichotomized changes in EDSS and other scales, will be tested with chi-square and proportion tests, or exact analogs if necessary. MSIS will be divided into patients with greater or less than a change of 7.5 (considered a significant change). Correlations between continuous scales will be examined, and compared between treatment groups. Events will also be compared to non-events, and combinations of (event outcome) will be tested for differences, using similar methods, in the unlikely situation there are enough events to permit meaningful statistical analysis (≥ 10 samples for an analysis group). Multiple groups can be tested with ANOVA methods for continuous outcomes, and with chi-square tests and logistic regression for binary outcomes.

Sample Size Estimation: Our null hypothesis for AIM #1, inferiority of the discontinue group, is a disease event proportion of 0.02 for the continue group, and 0.10 for the discontinue group. Our alternate hypothesis for the power calculation, non-inferiority of the discontinue group, is a disease event rate of 0.02 for both the continue and discontinue groups. Our study population consists of stable patients, so we expect the disease event rate to be very small for the continue group, and possibly the discontinue group as well. For a target alpha level of 0.025, a sample size of 112 per treatment group (225 total), would achieve 95% power for the non-inferiority test. For a single treatment group with 112 samples, if the true proportion is 0.02, then the upper bound of an exact confidence intervals can be expected to be less than 0.11 more than 95% of the time. Anticipating a dropout rate of approximately 9-15%, we plan to attempt to recruit 132 patients per treatment group (265 total).

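### For patients enrolled after about 1 September 2019, an EDSS rise first seen at T3 cannot be confirmed at 6 months, yet Aim 2 compares raw percentages with confirmed progression

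*Combined protocol and SAP*

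**What the plan says.** Section III.F.b (Aim #2) sets the progression rule: "this will be defined as an increase of at least one point, confirmed at 6 months, for those with a baseline EDSS" of 5.5 or lower, "or a change of at least 0.5 for those with EDSS of 6.0 or greater at baseline". The clause for the higher stratum does not repeat the confirmation requirement, but the outcome sentence speaks of confirmed progression throughout: "Outcomes assessed will include % of patients with confirmed progression in each group and mean change in EDSS in each group". Section III.F.c adds that "Binary outcomes, such as dichotomized changes in EDSS and other scales, will be tested with chi-square and proportion tests", or exact analogs.

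The full EDSS schedule is in section III.C: "They will be examined every 6 months at times T₀, T₁, T₂, T₃, and T₄", that is, at months 0, 6, 12, 18 and 24.

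The schedule is cut short for late entrants. Section III.C says that "Patients enrolled after July 31, 2019 will not complete the full two years of assessments", with follow-up ending on 1 September 2021. The Table 1 footnotes split these patients by the date of T3. If T3 is on or before 30 June 2021, the "participant should come in for an out of window T₄ visit before Sept. 1, 2021". If T3 is later, "participants will not come in for a T₄ visit, but will complete a NeuroQoL and Treatment Decision Question during T₃".

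Section III.F.b gives no rule for a rise first seen at T3 when T4 is early or absent, and none for unequal follow-up.

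**The concern.** A percentage with 6-month-confirmed progression has one meaning only if every patient in the denominator had the same opportunity to be confirmed. Here the plan itself creates two classes of patient. Those on the full schedule can have a rise at T1, T2 or T3 confirmed. Those entering late can have only a rise at T1 or T2 confirmed. If the definition is applied as written and everyone stays in the denominator, the late entrants add person-time in which progression can start but cannot count.

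The direction matters because Specific Aim 2 asks whether disability progression is no worse after discontinuation. Losing events from both arms shrinks the absolute difference between them, and a smaller difference is what that aim hopes to see. The cut-off was carried through to other assessments (Neuro-QoL, the Treatment Decision Question and the last MRI) but not to the EDSS confirmation rule.

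**Working it through.** **1. The plan's own figure.** The Sample Size Estimation text in section III.F states 80% power for Aims 2–3 with 112 per group, alpha 0.05, a control proportion of 0.3 and a ratio of 1.61. So p1 = 0.30, p2 = 0.30 × 1.61 = 0.483, and the mean is 0.3915. With a two-sided test and pooled variance under the null:

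power = Φ{[0.183 − 1.96 × √(2 × 0.3915 × 0.6085 / 112)] / √[(0.30 × 0.70 + 0.483 × 0.517) / 112]} = Φ{(0.183 − 0.1278) / 0.0641} = Φ(0.861) = 80.5%.

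The stated figure is reproduced.

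**2. The calendar.** Take T3 as enrolment plus 18 months. The latest permitted T4 is the nominal month-24 date or 31 August 2021, whichever is earlier.

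| Enrolled | T3 | Latest T4 | T3–T4 gap |
|---|---|---|---|
| 1 Aug 2019 | 1 Feb 2021 | 1 Aug 2021 | 181 days (full) |
| 1 Sep 2019 | 1 Mar 2021 | 31 Aug 2021 | 183 days (full) |
| 1 Oct 2019 | 1 Apr 2021 | 31 Aug 2021 | 152 days (about 5 months) |
| 1 Nov 2019 | 1 May 2021 | 31 Aug 2021 | 122 days (about 4 months) |
| 1 Dec 2019 | 1 Jun 2021 | 31 Aug 2021 | 91 days (about 3 months) |
| 30 Dec 2019 | 30 Jun 2021 | 31 Aug 2021 | 62 days (about 2 months) |
| From early Jan 2020 | after 30 Jun 2021 | none | no T4 |

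The T1–T2 and T2–T3 intervals stay at 6 months. T3 itself falls by the cut-off for anyone enrolled by about 1 March 2020.

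**3. Confirmable onset visits.** Full schedule: T1, T2 and T3, so 3. Truncated with T3 reached: T1 and T2, so 2. The loss is 1/3 of the confirmable onset visits.

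**4. Dilution with onset even over visits.** Let f be the truncated share of an arm and P the confirmed proportion under full follow-up. The observed proportion is (1 − f)P + f(2/3)P = P(1 − f/3). Both arms shrink by the same factor, so the absolute difference also falls by f/3 and the ratio does not change. For f = 10%, 20% and 30% (assumed values), the understatement is 3.3%, 6.7% and 10%.

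**5. A second onset assumption.** With constant risk per 6-month interval, a truncated patient's proportion is 1 − (1 − P)^(2/3). That takes 0.30 to 0.212 and 0.483 to 0.356. Mixing with the untruncated patients:

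| f | Control | Discontinue | Difference | Ratio | Power, n = 112 |
|---|---|---|---|---|---|
| 0 | 0.300 | 0.483 | 0.183 | 1.61 | 80.5% |
| 10% | 0.291 | 0.470 | 0.179 | 1.62 | 79.2% |
| 20% | 0.282 | 0.458 | 0.175 | 1.62 | 77.9% |
| 30% | 0.274 | 0.445 | 0.171 | 1.63 | 76.6% |

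At f = 30% the difference shrinks by 1 − 0.1714/0.183 = 6.3%, against 10% in step 4. The two assumptions agree on direction and on order of size.

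**The case against.** The strongest reply is that this is small and even-handed. Allocation is 1:1 and randomised within site, so truncation should fall about equally on both arms. The relative risk barely moves, and section III.F includes a relative-risk test among those powered for Aims 2–3. Aim 2 states no non-inferiority margin that a diluted difference could slip under. Every fixed-length trial has a last visit whose new rises cannot be confirmed; for full-schedule patients that visit is T4, and the cut-off only moves it one visit earlier for some. The documents give no accrual figures, so the truncated share is unknown. All of this stands, and it limits the point to modest dilution.

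Some stronger readings are tempting, and the documents do not support them:

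- A reader might infer that 6-month confirmation is impossible for all late entrants. It is not. T1 rises remain confirmable, as do T2 rises if T3 is reached, and August 2019 entrants can have a T4 at a full 24 months.
- A reader might infer that the plan counts these patients as non-progressors, or accepts a 2-month confirmation. It says neither. The first is one reading of a silent plan; the second goes against the stated definition, and 2 months is only the short end of the range.
- A reader might infer that Neuro-QoL is lost too. The Table 1 footnote moves it to T3 when there is no T4. Only patients enrolled after about 1 March 2020 would miss it, and no document shows that there were any.

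Balance does not answer the remaining point. Equal dilution of both arms still understates each arm's progression and the absolute difference between them.

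**Conclusion.** The point holds in this limited form. For enrolment after about 1 September 2019, the schedule shortens or removes the interval needed to confirm a T3 rise, and Aim 2 compares raw percentages as if follow-up were equal. Applied as written, with all patients in the denominator, this understates confirmed progression in both arms and the absolute difference by about f/3 under even onset (3% to 10% for f of 10% to 30%), and by somewhat less for the difference under constant interval risk. Power for the plan's 0.30 versus 0.483 contrast would fall from 80.5% to between 79.2% and 76.6% over the same range.

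This does not favour one arm through unequal truncation, and the relative risk is largely preserved. It rests on four assumptions: f is hypothetical; truncated patients reach T3; date of enrolment is unrelated to risk; and confirmation applies to both baseline EDSS strata. An unscheduled visit with an EDSS could supply a confirmation in individual cases, but follow-up for these patients ends at the same cut-off.

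**What to change.** In section III.F.b:

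1. Count a rise as confirmed only if the confirming EDSS is at least 6 months after the first one, less the visit window in Table 1. An early T4 that falls short of this does not confirm a T3 rise.
2. Replace the raw percentage with a Kaplan–Meier or discrete-time estimate of confirmed progression by arm. Censor each patient at the last visit at which a new rise could still have been confirmed: T3 with a full-interval T4, T2 when T4 is early or absent, and T1 if T2 is the last visit.
3. As a sensitivity analysis, report the proportion with onset by T2 confirmed by T3, to which everyone who reaches T3 can contribute on equal terms.

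The cost is a few sentences in the analysis plan. No visits, patients or data items are added, and the Neuro-QoL footnote need not change. The downside is that slightly fewer events count as confirmed and intervals widen slightly.
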